# 25.9.4. Numbers of Readings in the Low and High Ranges - Will Be Performed on Primary Datasets Only

Every effort to safely collect data in the low and high range via the hyperglycemic and hypoglycemic challenge will be made.

# 25.9.5. Difference Tables Comparing Sensor and Reference Readings - Will Be Performed on Primary Datasets Only

Number and percentage of paired data points within 10%, 15%, 20%, 30%, 40%, 50%, 60%, 70%, 80%, 90% and 100% of the reference method ( $YSI^{TM*}$  for in-clinic portion and meter BG for home-use portion) will be summarized.

Number and percentage of paired data within 10 mg/dL (0.6 mmol/L), 15 mg/dL (0.8 mmol/L), 20 mg/dL (1.1 mmol/L), 30 mg/dL (1.7 mmol/L), 40 mg/dL (2.2 mmol/L), 50 mg/dL (2.8 mmol/L), 60 mg/dL (3.3 mmol/L), 70 mg/dL (3.9 mmol/L), 80 mg/dL (4.4 mmol/L), 90 mg/dL (5.0 mmol/L) and 100 mg/dL (5.6 mmol/L) of the reference method (YSI™\* for in-clinic portion and meter BG for home-use portion) will be summarized.

# 25.9.6. Clarke Error Grid Analysis (EGA) of Paired Sensor and YSI™\* and Reference Values - Will Be Performed on Primary Datasets Only

## 1) Description

Clarke Error Grid Analysis (EGA) separates paired observations into five zones of clinical significance. The presence and severity of possible treatment error based on interstitial glucose assay evaluated by the sensor defines the five zones. Zone A represents the absence of treatment error, where the evaluation method and the reference method are within 20% of one another or in which both methods indicate hypoglycemia. Zone B represents cases where the two methods disagree by more than 20%, but do not lead to treatment error. Zones C, D, and E represent increasingly large and potentially harmful discrepancies between the evaluation and the reference method. If the method under evaluation has a high percentage (greater than (>)90%) of its pairs in Zones A and B, then it is considered clinically acceptable [Clarke et al, 1987].

### 2) Statistical analysis

Summary statistics (N, %) for each of the zones, as well as combined Zones A and B, will be calculated.

In order to evaluate differing levels of accuracy at various YSITM\* defined glucose levels, the number and percentage of paired observations falling into Zones A, B, A+B, C, D, and E will be provided by YSITM\* glucose ranges of 40-80 mg/dL (2.2 - 4.4 mmol/L), greater than (>) 80-120 mg/dL (4.4 - 6.7 mmol/L), greater than (>) 120-240 mg/dL (6.7 - 13.3 mmol/L), and greater than (>) 240 mg/dL (13.3 mmol/L).

All analysis performed using the Clarke Error Grid comparing the paired sensor and YSI™\* reference glucose values will be duplicated using the Continuous Error Grid [Clarke et al, 1987] and the Consensus Error Grid [Parkes et al, 2000].

# 25.9.7. Precision Analysis - Will Be Performed on Primary Datasets Only

Precision analysis will be performed for the two sensors worn by the same subject in the same location.

# 25.9.8. Comparison of CGM Performance to Reference under conditions leadings to Alert - Will Be Performed on Primary Datasets Only

[figure not shown]
The alert will be triggered when the sensor BG value reaches the threshold glucose value. Predictive alerts will be evaluated by using the predicted sensor BG value based on current sensor BG and sensor BG readings within the previous 30 minutes.

In the in-clinic portion, the threshold and predictive alert analysis will be performed retrospectively with theoretical hypoglycemia threshold setting at 50 mg/dL (2.8 mmol/L), 60 mg/dL (3.3 mmol/L), 70 mg/dL (3.9 mmol/L), 80 mg/dL (4.4 mmol/L), 90 mg/dL (5.0 mmol/L) and 100 mg/dL (5.6 mmol/L) and theoretical hyperglycemia threshold setting at 180 mg/dL (10.0 mmol/L), 220 mg/dL (12.2 mmol/L), 250 mg/dL (13.9 mmol/L) and 300 mg/dL (16.7 mmol/L).

The threshold alert performance will be evaluated for in-clinic portion by true alert rate, missed alert rate and false alert rate within 15 and 30 minute windows of the reference event. Predictive alert performance will only be evaluated for the in-clinic portion by true predictive alert rate, missed predictive alert rate and false predictive alert rate within 15 and 30 minute windows. All reference BG values will be used, including those less than (<) 40 mg/dL (2.2 mmol/L) and greater than (>) 400 mg/dL (22.2 mmol/L).

The comparison of CGM performance to reference under conditions leading to alert will be evaluated by true alert rate, missed alert rate and false alert rate within 15 and 30 minutes window of the reference event.

The alert rates will be defined as follows:

Alert Rate Type	Column Label	Label Definition
Detection Rate	Hypo/Hyper Events Correctly Detected (%)	The device alarmed at the specified CGM settings within 30 minutes (or 15 minutes) before or after the reference blood glucose value (YSI™* or SMBG) goes below (for hypo) or above (for hyper) the specified CGM setting levels.
Missed Detection Rate	Hypo/Hyper Events Not Detected (%)	The device did not alarm at the specified CGM settings within 30 minutes (or 15 minutes) before or after the reference blood glucose value (YSI™* or SMBG) goes below (for hypo) or above (for hyper) the specified CGM setting levels.
True Alert	Alerts Verified by Hypo/Hyper Events (%)	There is at least one reference blood glucose value (YSI™* or SMBG) goes below (for hypo) or above (for hyper) the specified CGM setting levels within 30 minutes (or 15 minutes) before or after the sensor alarmed at the specified alert settings.
False Alert	False Alerts (%)	There is no reference blood glucose value (YSI™* or SMBG) goes below (for hypo) or above (for hyper) the specified CGM setting levels within 30 minutes (or 15 minutes) before or after the sensor alarmed at the specified alert settings.

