#### **10.2.1.6.4.1** Blood Glucose Monitoring During the YSI™\* FST

The frequency of blood draws for YSI™\* FST sampling is dependent on the average value of YSI-B and YSI-W probes of the previous sample, according to the following ranges:

- less than (<) 75 mg/dL (4.2 mmol/L); every 5 minutes (window of 3-8 minutes)
- greater than or equal to (≥) 75 mg/dL (4.2 mmol/L); every 15 minutes (window of 7-23 minutes)

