#### **10.2.1.6.4.2** YSI™\* FST Not Available (For Example, IV Occlusion)

In the event that YSI™\* blood glucose values are not immediately available, for safety purposes, the investigational center may use the subject's CONTOUR® NEXT LINK 2.4 study meter (**US only**)/ CONTOUR® PLUS study meter (**China only**) to measure glucose. The fingerstick glucose values will be recorded on the appropriate eCRF and not used for analysis.

Venous blood samples should still be drawn for YSI™\* FST.

10976639DOC Version D

Page 79 of 170

Medtronic

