#### Ages 2 - 6 years

The frequency of blood draws for SMBG FST sampling is dependent on the value of the previous sample, according to the following ranges:

- less than (<) 70 mg/dL (3.9 mmol/L); every 5 minutes (window of 3-8 minutes)
- 70-80 mg/dL (3.9-4.4 mmol/L); every 15 minutes (window of 7 -23 minutes)
- greater than (>) 80 mg/dL (4.4 mmol/L); every 30 minutes (maximum of 45 minutes)

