True Alert	Alerts Verified by Hypo/Hyper Events (%)	There is at least one reference blood glucose value (YSI™* or SMBG) goes below (for hypo) or above (for hyper) the specified CGM setting levels within 30 minutes (or 15 minutes) before or after the sensor alarmed at the specified alert settings.

The alert rates will be defined as follows:

CIP330 Statistical Analysis Plan			Form	
	Medtronio			
Alert Rate Type	Column Label	Label Definition		
False Alert	False Alerts (%)	glucose value (YSI [™] below (for hypo) or the specified CGM 30 minutes (or 15 r after the sensor ala	There is no reference blood glucose value (YSI™* or SMBG) goes below (for hypo) or above (for hyper) the specified CGM setting levels within 30 minutes (or 15 minutes) before or after the sensor alarmed at the specified alert settings.	

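### The false-alert definition scores an alert as false even when its window holds no reference reading (minor; arises with late or missed samples)

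*Protocol*

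**What the plan says.** The alert analysis runs on the primary datasets only: "In the in-clinic portion, the threshold and predictive alert analysis will be performed retrospectively", at six hypoglycemia settings (50 to 100 mg/dL) and four hyperglycemia settings (180 to 300 mg/dL), with windows of 15 and 30 minutes.

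An alert is true if "There is at least one reference blood glucose value" beyond the setting falls in the window. It is false if "There is no reference blood glucose value (YSI™* or SMBG) goes below (for hypo) or above (for hyper) the specified CGM setting levels" in that window. The SAP row opens the same way, "There is no reference blood glucose value (YSI™* or SMBG", and adds no further condition. The two definitions are exact complements, and there is no third category.

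Reference sampling differs by age. At ages 7-80, YSI samples at or above 75 mg/dL are due "every 15 minutes (window of 7-23 minutes"), and below that every 5 minutes. At ages 2-6 the in-clinic reference is SMBG, and the sparsest band is "greater than (>) 80 mg/dL (4.4 mmol/L); every 30 minutes (maximum of 45 minutes"). These children fall within pediatric primary Datasets 2 and 3, labeled 2 to 17 years.

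**The concern.** An alert can fail to meet the true-alert definition for two reasons: readings were taken nearby and none crossed the setting, or no reading was taken nearby. Only the first is evidence against the sensor. The definition scores both as false, so the rate mixes device performance with sampling density.

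The false-alert and true-alert rates describe how far an alarm can be trusted. In the pediatric datasets, any inflation would come mostly from the most sparsely sampled children, who are pooled with YSI-referenced ages 7-17.

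**Working it through.** The documents give no alert rate, margin or sample size for this analysis, so there is no figure of the plan's own to reproduce. The stated power for 100 subjects concerns the agreement endpoint.

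**Inputs**
- Half-window w: 15 or 30 minutes (protocol 25.9.8).
- YSI gap at or above 75 mg/dL: 15 minutes, at most 23 (protocol 10.2.1.6.4.1; the same for ages 7-13 in 11.2.1.6.2.1).
- SMBG gap above 80 mg/dL, ages 2-6: 30 minutes, at most 45 (protocol 11.2.1.6.2.1).
- Missed samples: under protocol section 18 a single missed sample is not a deviation, and neither are samples lost to IV or YSI problems. Nothing is imputed (protocol 25.6, SAP 7.4). One missed YSI sample gives a gap of 30 to 46 minutes (2 × 15 to 2 × 23), and two give 45 to 69 (3 × 15 to 3 × 23). One missed SMBG at ages 2-6 gives 60 to 90 (2 × 30 to 2 × 45).

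**Share of a gap with no reading in the window.** Between two readings g minutes apart, a time point is uncovered if it lies more than w from both. The share is max(0, g − 2w)/g.

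| Situation | Gap (min) | ±15 | ±30 |
|---|---|---|---|
| YSI on schedule | 15 to 23 | 0% | 0% |
| SMBG ages 2-6, on time | 30 | 0% | 0% |
| SMBG ages 2-6, late | 35 | 5/35 = 14% | 0% |
| SMBG ages 2-6, late | 40 | 10/40 = 25% | 0% |
| SMBG ages 2-6, latest allowed | 45 | 15/45 = 33% | 0% |
| YSI, one missed | 30 to 46 | 0% to 16/46 = 34.8% | 0% |
| YSI, two missed | 45 to 69 | 33.3% to 39/69 = 56.5% | 0% to 9/69 = 13.0% |
| SMBG ages 2-6, one missed | 60 to 90 | 50% to 60/90 = 66.7% | 0% to 30/90 = 33.3% |

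**Effect on the rate.** Let f be the false rate among alerts that can be checked, and e the share of alerts with an empty window. The rule reports f(1 − e) + e, which is never below f. The values below are illustrative, because the documents supply neither f nor e.

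| f | e = 5% | e = 10% | e = 33.3% |
|---|---|---|---|
| 10% | 14.5% | 19% | 40% |
| 20% | 24% | 28% | 46.7% |
| 30% | 33.5% | 37% | 53.3% |

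The last column would need every alert to fall in a gap of maximum length, so it is an upper marker and not an expectation.

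**Session edges.** Near the start or end of a session the window runs past the sampled period. It is then truncated, and normally not empty. A truncated window misleads only if the one crossing lies in the unsampled part, and nothing in the documents says how often that would happen.

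**The case against.** The strongest reply is that the exposure is narrow. With YSI on schedule, no in-session window is empty at either width. The same holds for ages 2-6 sampled at the scheduled 30 minutes, and at ±30 even for the permitted 45. At or below 80 mg/dL their sampling tightens to 15 or 5 minutes. All of this stands, and it sets the size of the point. It does not remove it. The interval follows the previous reading, so a fast fall can trigger an alarm before the next fingerstick. All four hyperglycemia settings also lie in the sparse band.

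It can also be said that reporting both windows shows the sensitivity. It does so only in part, because the ±15 to ±30 difference mixes tolerance for timing with loss of coverage.

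It is not certain that ages 2-6 enter this analysis. Protocol 25.6 and SAP 7.1.3 define the efficacy population by a paired sensor and YSI value, which these children lack. The dataset labels, and protocol 25.7 on SMBG agreement for this group, point towards inclusion.

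Three stronger readings are tempting and not supported:
- **That barred fingersticks enter the alert reference.** SMBG is the planned reference at ages 2-6, and protocol 11.2.1.6.2 says those values are analyzed. For fallback readings at ages 7-80 the protocol says "The fingerstick glucose values will be recorded on the appropriate eCRF and not used for analysis", and section 16 excludes alternate point-of-care readings. The statement "All reference BG values will be used" goes on to extreme glucose values and does not readmit them. What remains is a label not tied to age.
- **That the whole window must lie inside the session.** That would discard alerts already verified by an in-session crossing.
- **That detected and missed rates share the defect.** They are anchored on reference events, so a reading exists by construction.

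**Conclusion.** The point holds in a limited form. As written, an alert with no reference reading in its window is a false alert. The bias has one direction: false-alert rate up, true-alert rate down. It is nil inside a session sampled on the YSI schedule. At ages 2-6 it is confined to ±15 minutes unless a sample is missed, and reaches 33% of the gap at the longest permitted interval. With missed or lost samples it can reach any age, and for the longer gaps it appears at ±30 as well.

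The shares assume alert times spread evenly within a gap. Their effect on any reported rate cannot be estimated from the documents, so it would go too far to say that the alert rates as a whole are mis-measured. The ages 2-6 part also assumes that these children are in the alert analysis. The analysis is descriptive, on primary datasets only, and study success rests on the primary endpoint. The severity is minor.

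**What to change.** In protocol 25.9.8 and SAP 7.9.1.4.5, use three categories for each setting and window:
- **True:** at least one reference reading in the window crosses the setting.
- **False:** the window holds at least one reference reading and none crosses.
- **Unevaluable:** the window holds no reference reading. Exclude these from the true/false denominator and report their number.

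An alert near a session edge is then classified on whatever readings its window contains. Leave the detected and missed definitions as they are.

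As a clarification, name the in-clinic alert reference as YSI for ages 7-80 and SMBG FST values for ages 2-6. This agrees with protocol 10.2.1.6.4.2, 11.2.1.6.2 and 11.2.1.6.2.2. Section 16 should be worded so that its exclusion of alternate point-of-care values during SMBG FSTs cannot be read as covering the SMBG FST readings themselves.

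The cost is a few sentences in each document and one filter in the alert program. No new data are needed, and denominators shrink only by the number of alerts that had no reading to judge them.

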# 25.9.9. Other Accuracy Analyses - Will Be Performed on Primary Datasets Only

A correlation between the sensor and YSITM\* values will be performed. As this statistic ignores any data dependency, it will be used only as a descriptive measure of association.

A linear model, in which YSITM\* is predicted by sensor values, using a repeated measures model, will be performed. The models solution will provide the intercept and slope, while adjusting for dependence in the data within day. An intercept of 0, along with a slope of 1, would indicate the absence of bias in predicting YSITM\* from sensor readings. The residuals of the model will be inspected to determine if transformation of either variable is required.

Bland-Altman plots, with 95% confidence interval (CI), will be provided. The paired differences between the sensor and  $YSI^{TM*}$  rating will be plotted against the X-axis reference of mean  $YSI^{TM*}$  and sensor values.

# CIP330 Clinical Investigation Plan 10976639DOC Version D Page 148 of 170 Medtronic

Descriptive subgroup analysis of DS5 sensor performance (20% mean agreement rate (±20 mg/dL [1.1 mmol/L] when SG less than (<) 80 mg/dL [4.4 mmol/L]) will be performed in the following cohorts:

- Diabetes cohorts based on insulin requirement:
  - Type 1 insulin requiring
  - Type 2 insulin requiring
  - o Type 2 non-insulin requiring
- Diabetes cohorts based on Centers for Disease Control and Prevention (CDC) classification for younger than 20 years old:

A description of the following 4 groups will be performed:

- Underweight subjects (less than (<) 5th percentile)
- Normal weight subjects (5th percentile to less than (<) 85th percentile)
- Overweight (85th to less than (<) the 95th percentile)
- Obese subjects (greater than or equal to (≥) the 95th percentile)
- Diabetes cohorts based on BMI according to WHO criteria [World Health Organization, 2011] for subjects equal to or greater than 20 years old:

A description of the following 5 groups will be performed:

- Underweight subjects (BMI less than (<)18.5 kg/m²)

- Normal weight subjects (BMI 18.5 to 24.99 kg/m²)
- Overweight and obese subjects (BMI 25.00 to 40 kg/m²)
  - Overweight subjects (BMI 25.00 to 29.99 kg/m²)
  - Obese subjects (BMI 30.00 to 39.99 kg/m²)
- Morbidly obese subjects (BMI greater than or equal to (≥)40 kg/m²)
- Diabetes cohorts based on prior real-time CGM experience (by self-report)
  - CGM naïve
  - CGM experienced
- Diabetes cohorts based on prior pump experience (by self-report)

10976639DOC Version D Page 149 of 170

- Pump naïve
- Pump experienced

#### Diabetes cohorts based on HbA1c:

- Baseline HbA1c (by certified National Glycohemoglobin Standardization Program, NGSP, method) will be collected:
  - A description of the following 3 groups will be performed: HbA1c less than (<) 7%, HbA1c 7-9%, HbA1c greater than (>) 9%
- Quartile comparison (lowest to the highest) based on HbA1c

### • Diabetes cohort based on exercise activity:

 Per Investigator's discretion, subjects may participate in the exercise in order to obtain low glucose values.

All analysis follow the definitions provided in: Performance Metrics for Continuous Interstitial Glucose Monitoring: Approved Guideline, CLSI POCT05-A [Klonoff et al. 2008].

# 25.9.10. Home-Use Portion Data Analysis - Will Be Performed on Primary Datasets Only

Data from the home-use portion will be described. Analysis will include but not be limited to: 20% mean agreement rate (±20 mg/dL [1.1 mmol/L] when SG less than (<) 80 mg/dL [4.4 mmol/L]) for all fingersticks (capillary SMBG) collected, Clark Error Grid, other accuracy analysis, absolute relative difference (ARD), bias, correlation between sensor and SMBG and Bland-Altman plots. In addition, 20% mean agreement rate (±20 mg/dL [1.1 mmol/L] when SG less than (<) 80 mg/dL [4.4 mmol/L]) will be described by subgroups of: age, YSITM\* FST, diabetes classification, BMI/weight, CGM experience, HbA1c and exercise activity (if applicable).

## 25.10. Safety

Descriptive summary will be used to characterize adverse events:

- Skin assessment at sensor insertion sites
- All adverse events

10976639DOC Version D

Page 150 of 170 Medtronic

### 25.11. Device Deficiencies

Descriptive device deficiencies will include all reports of sensor damage, breakage or fracture.

# 25.12. Subject Feedback

Descriptive summary will be used to characterize study survey results.

# 26. Ethics

# 26.1. Statement(s) of Compliance

#### IRB/EC

This CIP, any subsequent amendments to this CIP, the ICF and assent form (if applicable), subject materials and any form of subject recruitment information (e.g. advertisements) relating to this study will be approved by the responsible IRB/EC in accordance with 21 CFR Part 56 **(US only)** NMPA Order No. 25 **(China only)** and local regulatory requirements as applicable. The investigational center will not initiate any subject activities until IRB/EC approval has been granted, the sponsor has cleared the investigational center to begin the study, and the investigational center staff has been appropriately trained to conduct the study.

## **China only:**

This study is a pre-market clinical trial for product registration. The study will be conducted in accordance with the laws and regulations of China, including any future applicable laws and regulations in China.

### Regulatory Compliance

### **US only**:

This clinical study will be conducted in compliance with the Clinical Investigation Agreement; United States Code of Federal Regulations (CFR) Title 21 Part 50 (Protection of Human Subjects), Part 54 (Financial Disclosure by Clinical Investigators), Part 11 (Electronic Records; Electronic Signatures), Part 812 (Investigational Device Exemptions), and Part 56 (Institutional Review Boards) and all other applicable federal and local regulatory requirements.

#### China only:

To protect the rights and welfare of patients, this clinical study will be conducted in compliance with the latest version of the Declaration of Helsinki, the Clinical Trial Agreement and CIP, the laws and regulations of China including NMPA Order No. 25 (which includes Good Clinical Practice for Medical

# CIP330 Clinical Investigation Plan 10976639DOC Version D Page 151 of 170 Medtronic

Devices and the exclusion stated below), Announcement of NMPA on Filing of Medical Device Clinical Trial (2015, No.87) and also including applicable data protection laws. Investigational centers will also comply with any additional EC requirements applicable. As this is a multiple center global study, per agreement by Center for Medical Device Evaluation (CMDE), the requirements of the leading site and coordinating investigator(s) will not be applicable for the study (exception to the NMPA Order No.25).

## All regions:

The study will also be conducted in compliance with the principles of good clinical practice (GCP) meaning that the study design, conduct, performance, monitoring, auditing, recording, analysis and reporting will assure that the data and results are credible and accurate and that the rights, safety and well-being of subjects are protected. GCP includes review and approval by an independent ethic committee (IEC)/ IRB before initiating the investigation, ongoing review of the investigation by an IEC/IRB and obtaining and documenting the freely given informed consent of the subject (or the subject's legally authorized representative) before their participation in the investigation.

The ethical principles that have their origin in the Declaration of Helsinki have been implemented in this clinical study by means of the informed consent and assent (if applicable) process, IRB/EC approval, study training, clinical trial registration, preclinical testing, risk benefit assessment, publication policy, etc.

If the subject is below 18 years of age, he/she should be informed about the study to the extent compatible with the subject's understanding. Per IRB/EC, if the subject could give consent to decisions about participation in research, the investigator must obtain that consent in addition to the consent of their legally authorized representative or quardian.

